1.0 TRIAL SUMMARY

Abbreviated Title	MK-8583 Single Dose Study in HIV-1 Infected Patients
Sponsor Product Identifiers	MK-8583
Trial Phase	Phase Ib
Clinical Indication	Treatment of HIV-1 Infection
Trial Type	Interventional
Type of control	Historical placebo control
Route of administration	Oral
Trial Blinding	Unblinded Open-label
Treatment Groups	Up to three panels (Panel A, B, and C) of 6 subjects each will receive a single dose of MK-8583.
Number of trial subjects	Approximately 18 subjects will be enrolled.
Estimated duration of trial	The Sponsor estimates that the trial will require approximately 7 months from the time the first subject signs the informed consent until the last subject's last study-related phone call or visit.
Duration of Participation	Each subject will participate in the trial for approximately 8 weeks from the time the subject signs the Informed Consent Form (ICF) through the final contact. After a screening phase of approximately 4 weeks, each subject will be receiving assigned treatment for 1 day. After the end of treatment each subject will be followed for approximately 28 days. Subjects choosing to forgo follow-on combination anti-retroviral therapy (ART) may also be asked if they wish to continue to participate in observational monitoring beyond 28 days.

A list of abbreviations used in this document can be found in Section 12.5.

2.0 TRIAL DESIGN

2.1 Trial Design

This is an open-label, single-dose, multiple panel trial to evaluate the safety, tolerability, pharmacokinetics (PK), and anti-retroviral therapy (ART) activity of MK-8583 monotherapy in ART-naïve, Human Immunodeficiency Virus type 1 (HIV-1) infected subjects. The primary study endpoints are the safety and tolerability of MK-8583 and the change in plasma HIV-1 RNA (log₁₀ copies/mL) compared with historical placebo data. This study will be conducted in conformance with Good Clinical Practices.

Up to three panels of 6 subjects each will be enrolled in a sequential manner. All doses of study drug will be administered following at least an 8-hour fast. In each panel, subjects will receive a single dose of MK-8583. Safety procedures and biological specimen collections will occur at designated time points. Subjects in Panel A will receive a single oral dose of MK-8583 100 mg. The exact dose administered in Panels B and C will be selected following review of all available safety, PK and viral dynamic data from prior panel(s); the dose will not exceed 150 mg. There will be an interval of time between dosing of panels to allow for

review of safety, PK, and viral dynamic data to inform dose selection in the following panel. It is estimated that this review will take approximately 30-40 days.

Initiation of ART: At a designated time following administration of study drug, subjects will be encouraged to initiate an ART regimen. The exact timing and regimen will be decided by the subject in consultation with his/her physician, but ART initiation will not occur before Day 10 post-dose (see Section 5.5). Once initiated, the duration of suppressive ART is recommended to be at least ~25 days, or approximately 5 half-lives of tenofovir diphosphate (TFV-DP) in peripheral blood mononuclear cells (PBMCs). To lessen the chance of HIV resistance mutations, the Sponsor recommends that ART initiation occurs on or before Day 14 post-dose. The Sponsor will not provide this therapy.

The initiation of follow-on ART is not a requirement for participation in the study. All subjects will be followed for safety monitoring for a maximum of approximately 28 days after dosing of MK-8583. If subjects start ART as planned, on Day 10 through 14 after dosing, the final blood draw for viral load (VL), viral resistance, or PK will occur on the day of ART initiation (prior to receiving the first dose of ART).

If subjects do not initiate ART, the Investigator may ask to continue regular blood draws for PK assessments, VL changes, and viral resistance for up to ~28 days post-dose. Subjects choosing to forgo follow-on ART may also be asked if they wish to continue to participate in observational monitoring of VL and viral resistance beyond 28 days. The timing of these blood draws beyond Day 28 will first be discussed with the Sponsor.

If subjects initiate an ART regimen that does not include tenofovir disoproxil fumarate (TDF) or tenofovir alafenamide fumarate (TAF), the Investigator may ask to continue regular blood draws for PK assessments for up to ~28 days post-dose. The timing of these blood draws beyond Day 28 will first be discussed with the Sponsor.

Specific procedures to be performed during the trial, as well as their prescribed times and associated visit windows, are outlined in the Trial Flow Chart - Section 6.0. Details of each procedure are provided in Section 7.0 – Trial Procedures.

Because this is a Phase I assessment of MK-8583 in humans, the pharmacokinetic, pharmacodynamic and safety profiles of the compound are still being elucidated. This protocol is therefore written with some flexibility to accommodate the inherent dynamic nature of Phase I clinical trials. Please refer to Section 7.1.5 – Visit Requirements for examples of modifications permitted within the protocol parameters.

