MK-8583 was assessed in a single rising-dose study in healthy subjects. Following oral administration, MK-8583 was rapidly absorbed (time to maximum plasma concentration [T_{max}] ~ 0.5 hour) and rapidly eliminated from the plasma (terminal half-life [t_{1/2}] of 0.2 to 0.4 hours). Prodrug exposure was dose-proportional at doses ≥ 40 mg. Plasma TFV exposure was also dose-proportional, with a T_{max} of 1 to 4 hours and a t_{1/2} in the range of 19 to 30 hours. TFV-DP in PBMCs exhibited a median T_{max} of 4 to 24 hr and a terminal t_{1/2} ranging from 65 to 136 hours. The PBMC TFV-DP AUC increased approximately dose-proportionally, and the C_{max} increased somewhat more than dose-proportionally. Food somewhat lowered peak and extent of exposure of PBMC TFV-DP (GM fed/fasted ratio of 0.83 for AUC_{0-inf}, 0.32 for maximum concentration [C_{max}], 0.47 for C_{168hr}). Elimination of plasma MK-8583 was monophasic, while elimination of plasma TFV was biphasic. PBMC TFV-DP presented monophasic elimination, but showed signs of biphasic elimination at higher doses.

Single oral doses of MK-8583 up to 150 mg were generally well tolerated. No SAEs, events of clinical interest (ECIs), or deaths were reported. A total of 24 subjects enrolled in the trial. No trends were observed between AE incidence and increasing dose levels, and there were no AE findings consistent with renal or bone toxicity. No clinically meaningful trends were observed for changes in clinical laboratory values, vital signs (VS), or ECGs as a function of dose or treatment.

Please refer to the Investigator's Brochure (IB) for more detailed information on MK-8583.

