4.2.2 Rationale for Dose Selection/Regimen/Modification

As this is a Phase I assessment of MK-8583 in humans, and the PK, PD and safety profiles of the compound are still being evaluated, modifications to the dose or dosing regimen may be required to achieve the scientific goals of the trial objectives and/or to ensure appropriate safety monitoring of the trial subjects. Details of allowed modifications are provided in Section 7.1.5.5 - Trial Design/Dosing/Procedures Modifications Permitted within Protocol Parameters.

The doses tested in this study will evaluate the effectiveness of MK-8583 in suppressing viral replication and will allow for assessment of potential differentiation in tolerability and efficacy. The study is specifically designed with an emphasis on collecting single dose viral dynamic data. Since only a single dose of MK-8583 will be administered to each subject, risk of resistant strain emergence is minimal.

Doses selected for this study are projected to fall within the expected clinical dose range. A dose that achieves a TFV-DP C168h in PBMCs of 100 nM is projected to be efficacious. This is approximately the Day 7 PBMC Ctrough achieved with daily dosing of TDF 300 mg (the therapeutic dose) for one week, which results in a 0.5 log₁₀ reduction in VL [4]. In the single-rising dose study of MK-8583 in healthy subjects, a PBMC TFV-DP C168h target of 100 nM was achieved at doses ≥ 40 mg of MK-8583.

To maximize the chances of efficacy and minimize the impact of inter-subject PK variability, a 100 mg dose of MK-8583 will be administered to subjects in Panel A. This dose is expected to achieve PBMC TFV-DP concentrations well above that of the projected minimum effective dose of 40 mg (see above) while maintaining a plasma concentration of the TFV metabolite (the relevant correlate of toxicity) at $\leq \frac{1}{2}$ the exposure seen at the preclinical no-observed-adverse-effect level (NOAEL).

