There will be a break between dosing of panels to allow for review of all available safety, PK, and viral dynamic data to inform dose selection in the following panel. It is estimated that this review will take approximately 30-40 days. Because plasma MK-8583, plasma TFV, and PBMC TFV-DP PK data from healthy subjects are expected to be similar to that of HIV-1 infected subjects, PK data from single doses administered to healthy subjects in Protocol 001 will also be used to aid in the selection of doses for the present study to ensure that plasma MK-8583 levels do not exceed the exposure cap.

The specific dose selected for Panel B will depend on data from Panel A. Assuming PK data indicate that higher exposures maintain safety margins, a higher dose may be tested to see if it delivers greater efficacy. Alternatively, if 100 mg generates exposures in HIV-infected subjects that are higher than what was seen in healthy subjects, or if safety concerns arise, a lower dose may be tested. After Panel B, the Sponsor will assess the utility of testing a third dose in Panel C to further explore PK, PD, and the safety profile of the compound.

Additionally, safety data through at least 168 hours post-dose, including AEs, standard laboratory safety tests, VS, and 12-lead ECGs, physical examinations (PEs) will be reviewed by the Sponsor and the investigator prior to dose escalation, and the decision to proceed to a new dose level will be based upon acceptable safety of MK-8583 at the previous dose. The doses selected for Panels B and C in this study will not exceed the maximum dose of 150 mg previously administered to healthy subjects.

The reduction in VL for each dose level will be compared to historical placebo data from clinical trials previously conducted by the Sponsor. Given the overall favorable safety profile of MK-8583 in preclinical and clinical testing to date, a placebo control to minimize investigator and subject bias with respect to adverse experiences is not deemed necessary.

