5.5 Concomitant Medications/Vaccinations (Allowed & Prohibited)

If a subject does not discontinue all prior medications within 14 days or 5 half-lives of starting the trial, he/she may be included in the study if the investigator can rationalize that the specific use of a prior medication is not clinically relevant within the context of the trial.

Concurrent use of any prescription or non-prescription medication, or concurrent vaccination, during the course of the trial (i.e., after randomization or treatment allocation) must first be discussed between the investigator and Sponsor prior to administration, unless appropriate medical care necessitates that therapy or vaccination should begin before the investigator and Sponsor can consult. The subject will be allowed to continue in the trial if both the Sponsor and the investigator agree.

Paracetamol/acetaminophen may be used for minor ailments without prior consultation with the Sponsor.

Initiation of ART: All subjects will be encouraged to initiate ART some interval after their dose of MK-8583. The exact timing and regimen will be decided by the subject in consultation with his/her physician, but ART initiation will not occur before Day 10 (240 hours post-dose). This timing is required to gather full efficacy data for this novel long-acting anti-retroviral compound and is consistent with prior anti-retroviral monotherapy proof-of-concept trials, in which low-dose anti-retroviral monotherapy has been administered for as long as 28 days [10] and with European Medicines Agency (EMA) guidance [5]. If the physician and/or Investigator believe there is a strong indication to start ART before Day 10, this should be discussed with the Sponsor prior to starting, as with other concomitant medications (see above).

To lessen the chance of HIV resistance mutations developing, the Sponsor recommends that ART initiation occurs before PBMC TFV-DP concentrations fall below 100 nM. (100 nM is set as the lower limit because this is the steady-state Ctrough of TDF.) In Panel A (100 mg dose), the PBMC TFV-DP concentration is expected to fall below 0.1 μM after 4 half-lives, or ≥ 14 days, and therefore it is recommended that ART is initiated on or before Day 14. In subsequent panels, the Sponsor will provide the site with written guidance, prior to the start of dosing, as to the time when PBMC TFV-DP concentrations are expected to fall below the 100 nM lower limit.

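### Does the Day 14 recommendation for starting ART in section 2.1, which names no panel, conflict with section 5.5, which derives Day 14 for Panel A only?

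*Combined protocol and SAP*

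**What the plan says.** Section 2.1 (Trial Design) describes all three panels together. To limit resistance mutations, "the Sponsor recommends that ART initiation occurs on or before Day 14 post-dose". It then describes the expected course: "If subjects start ART as planned, on Day 10 through 14 after dosing", the last viral load, resistance or PK draw falls on the day ART starts. Neither sentence names a panel. The cross-reference to section 5.5 is attached to the sentence on the Day 10 minimum, not to the Day 14 sentence.

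Section 5.5 gives the reasoning. ART should start before TFV-DP in PBMCs falls below 100 nM. For Panel A this is expected "after 4 half-lives, or ≥ 14 days, and therefore it is recommended that ART is initiated on or before Day 14". For the rest, "In subsequent panels, the Sponsor will provide the site with written guidance, prior to the start of dosing", on when the 100 nM level is expected to be crossed. The same section sets the Day 10 minimum (240 hours), explains that it protects the efficacy data, and says that a strong indication to start sooner is to be discussed with the Sponsor.

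Section 4.2.2 leaves the later doses open. Panel B may go higher. If exposures exceed those in healthy subjects, "or if safety concerns arise, a lower dose may be tested". The ceiling is 150 mg.

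**The concern.** Section 5.5 makes the day depend on concentration, and therefore on dose. Section 2.1 gives one day for a trial whose second and third doses are not yet chosen. After a lower dose, the 100 nM level could be crossed before Day 14, or even before the Day 10 minimum. A reader who stopped at section 2.1 would then have a date that no longer serves its stated purpose. The sharpest form of the worry comes from section 4.2.2: "A dose that achieves a TFV-DP C168h in PBMCs of 100 nM is projected to be efficacious". A dose that only just met that target would be at the section 5.5 limit on Day 7, before the whole Day 10 to 14 window.

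The Panel A figure also invites a check, because section 4.1.2 reports "a terminal t_{1/2} ranging from 65 to 136 hours" and four half-lives at the short end come to less than 14 days. At stake would be the resistance rationale for the timing and, possibly, when viral load sampling ends.

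**Working it through.** **1. The plan's own figure.** Four half-lives in 14 days means 14 × 24 / 4 = 84 h, inside the 65 to 136 h of section 4.1.2. Counting from a Tmax of 24 h instead gives (336 − 24) / 4 = 78 h, also inside. Section 2.1 equates about 25 days with five half-lives, so 25 × 24 / 5 = 120 h, and four of those take 20 days, which agrees with at least 14. Over the full range, four half-lives run from 4 × 65 / 24 = 10.8 days to 4 × 136 / 24 = 22.7 days. No half-life is given for 100 mg, so the figure is compatible with the documents but cannot be confirmed from them.

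**2. How the day moves with dose.** This is an illustration, because no lower dose is stated. Assume single-phase decay, levels proportional to dose, and 100 mg reaching 100 nM at four half-lives. Then

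day = (t / 24) × [4 + log2(dose / 100)], with t the half-life in hours.

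| Dose | Half-lives | Day, t = 84 h | Day, t = 120 h | Range, t = 65 to 136 h |
|---|---|---|---|---|
| 40 mg | 2.68 | 9.4 | 13.4 | 7.3 to 15.2 |
| 50 mg | 3.00 | 10.5 | 15.0 | 8.1 to 17.0 |
| 100 mg | 4.00 | 14.0 | 20.0 | 10.8 to 22.7 |
| 150 mg | 4.58 | 16.0 | 22.9 | 12.4 to 26.0 |

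So one day does not follow from the 100 nM rule for every permitted dose. That much of the concern is right.

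**3. The Day 7 case.** Setting day = 7 gives log2(dose / 100) = 168 / t − 4. At 84 h this is −2, or 25 mg. At 120 h it is −2.6, or 16.5 mg. At 65 h it is about −1.42, or 37.5 mg. All lie below the 40 mg that section 4.2.2 calls the projected minimum effective dose. The case is an extreme and cannot be combined with the 40 mg row of the table.

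**4. The two sections together, by what the guidance might say.**
- A day from Day 10 to Day 14: a start by that day meets both sections.
- A day after Day 14: a start by Day 14 meets both. A later start meets the guidance but not section 2.1.
- A day before Day 10: this meets the minimum in both sections head on. Section 5.5 supplies the route, discussion with the Sponsor, and section 2.1 points to section 5.5 at exactly that sentence.

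**5. Sampling.** Section 5.5 sets no end of sampling. Section 2.1 and footnote m of the flow chart (all panels) tie the last viral load and resistance sample to the day ART begins. Footnote l allows PBMC samples up to the post-trial visit whether or not ART has begun. The panel scope of Day 14 does not enter.

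**6. Primary analysis.** Section 8.2.4 models the pre-dose and 168-hour values. The Day 10 minimum is 240 h, and 240 − 168 = 72 h. Even a sample taken at the end of the widest window that Table 6 lists at 168 h (24 h) falls at 192 h, 48 h before the minimum.

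**The case for a change.** The best case for a change is that the protocol has no rule saying which section prevails. When guidance is issued for Panel B or C, section 2.1 will still say Day 14. A lower dose is a foreseen option, and under the assumptions above 40 mg crosses 100 nM before Day 14 at both 84 h and 120 h. Cmax rose somewhat more than in proportion to dose (section 4.1.2), which would bring the low-dose days slightly forward. Aligning the wording would cost almost nothing.

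The difference in scope stands, and so does the dependence on dose. The harm does not follow. The guidance is due before dosing, so a site treating Panel B or C has a panel-specific expectation in hand and need not rely on the overview. Section 2.1 itself leaves the exact timing to the subject and physician. One of the two triggers for a lower dose in section 4.2.2 is that 100 mg gave higher exposure than expected. In that event, scaling down from the predicted 100 mg curve makes the crossing look too early. The half-life point shows a figure that is unconfirmed, not one that is wrong.

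**Conclusion.** No change to the plan follows. Sections 2.1 and 5.5 differ in scope: one gives Day 14 for the trial as a whole, the other for Panel A. The difference lies between an overview and the detailed section it summarises. For each later panel the two must be reconciled, and the written guidance that section 5.5 requires before dosing is the place where that happens. I take no view on which timing is right; that is for the sponsor and investigators.

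The size is a matter of wording. ART is optional, Day 14 is a recommendation, section 4.2.2 regards resistance risk after a single dose as minimal, and the primary endpoint precedes the earliest planned ART start by 72 h. No estimate, posterior probability or conclusion would change.

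This rests on two assumptions: that the guidance is issued as promised, and that any start before Day 10 stays an exception handled through section 5.5. The dose illustration further assumes proportional levels and single-phase decay. It shows the direction of the effect and predicts nothing for a particular panel.

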2.2 Trial Diagram

The trial design is depicted in [Figure 1](#) and [Table 1](#).

[figure not shown]

Figure 1 Trial Design Diagram

Table 1 Dose Plan

Panel ^a	Dose ^b
Panel A	100 mg
Panel B	≤ 150 mg
Panel C ^c	≤ 150 mg

^a In each panel, 6 subjects will receive a single dose of MK-8583.

^b The dose administered in Panels B and C will be determined following review of safety, PK, and viral load data from the previous panel(s) and will not exceed 150 mg. At least approximately 30-40 days will separate the administration of doses between panels to allow time for review of the previous panel safety, PK and viral load data.

^c A decision to enroll Panel C will be made upon completion of the previous panels and review of safety, PK, and viral load data.

3.0 OBJECTIVE(S) & HYPOTHESIS(ES)

3.1 Primary Objective(s) & Hypothesis(es)

- 1) **Objective:** To evaluate the anti-retroviral activity of MK-8583 in HIV-1 infected subjects relative to historical subjects receiving placebo.

Hypothesis: At a dose that is sufficiently safe and generally well tolerated, MK-8583 has superior anti-retroviral activity compared to placebo, as measured by change from baseline in plasma HIV-1 RNA (log₁₀ copies/mL) at 168 hours post-dose. That is, the true mean difference in the plasma HIV -1 RNA reduction from baseline between MK-8583 and placebo is at least 0.5 log₁₀ copies/mL.

- 2) **Objective:** To evaluate the safety and tolerability of MK-8583 in HIV-1 infected subjects.

3.2 Secondary Objective(s) & Hypothesis(es)

- 1) **Objective:** To evaluate the intracellular PK profile of TFV-DP and to determine PK parameter values (including AUC_{0-168hr}, T_{max}, C_{max}, C_{168hr}, and apparent terminal t_{1/2}) in PBMCs after administration of single oral doses of MK-8583 to HIV-1 infected subjects.

Hypothesis: The true geometric mean (GM) TFV-DP PBMC C_{168hr} is $\geq 0.1 \mu\text{M}$ for at least one dose level that also exhibits an acceptable safety and tolerability profile.

- 2) **Objective:** To characterize the single dose plasma PK profile of MK-8583 and to determine the PK parameter values (including AUC_{0-last}, AUC_{0-inf}, T_{max}, C_{max}, apparent terminal t_{1/2}, CL/F and V_z/F) after administration of MK-8583 to HIV-1 infected subjects.
- 3) **Objective:** To obtain the single dose plasma PK profile of TFV and to determine the PK parameter values (including AUC_{0-last}, AUC_{0-inf}, T_{max}, C_{max}, and apparent terminal t_{1/2}) after administration of MK-8583 to HIV-1 infected subjects.
- 4) **Objective:** To evaluate the PK-PD association of TFV-DP with viral load reduction.

3.3 Exploratory Objectives

- 1) **Objective:** To evaluate the relationship between dose and anti-retroviral activity of MK-8583.
- 2) **Objective:** To quantify PBMC levels of tenofovir monophosphate (TFV-MP).
- 3) **Objective:** To explore the relationship between genetic variation and response to the treatment(s) administered and mechanisms of disease. Variation across the human genome may be analyzed for association with clinical data collected in this study.

4.0 BACKGROUND & RATIONALE

4.1 Background

Refer to the Investigator's Brochure (IB)/approved labeling for detailed background information on MK-8583.

